The rationale for up to 11 months of therapy (9 months off milk and up to 2 months after milk reintroduction) is based on preliminary data for IgE-mediated food allergy with efficacy being generally evaluated after 12 months of epicutaneous therapy (EPIT). In addition, the pre-clinical data in the pig model of eosinophilic gastritis was seen after around 3 months of therapy. It was extrapolated that between 9 to 11 months of EPIT in this pilot study, would be adequate. After the third endoscopy at the end of the double-blind treatment period (Visit 10), the study will be extended by one additional year and all subjects will receive open-label Viaskin® Milk (500 µg of milk proteins) for up to 11 months. A fourth endoscopy with biopsies for research will be done at the end of the open-label treatment period (Visit 16). The extension of the study will permit to assess the long-term safety and efficacy of Viaskin® Milk for up to 22 months of treatment in subjects with milk-induced Eosinophilic Esophagitis.

For EoE, there is no definitive treatment to mitigate disease progression of disease except for avoidance. In the standard of care, it is considered normal to periodically reintroduce foods to see if the subject has outgrown it. The first two endoscopies will be standard of care. The first endoscopy will permit to confirm the diagnosis of EoE and the second endoscopy will be used to confirm the diagnosis of milk-induced EoE. In our typical standard of care, the endoscopy will be performed, after treatment with proton pump inhibitor. The first endoscopy (standard of care) includes biopsy of esophagus, stomach and duodenum to ensure that eosinophilic inflammation is isolated to the esophagus. The second (standard of care), third (research) and fourth (research) endoscopies will include biopsies of esophagus only.

For safety purposes and to minimize risk, the first four patients will be 8-17 years old and after these patients are randomized, we will open the study to all ages 4-17 years old.

Table 2: Upper Endoscopies with Biopsies

1	Initial Endoscopy	Standard of Care	Biopsies of esophagus, stomach and duodenum
2	Second Endoscopy	Standard of Care	Biopsies of esophagus
3	Third Endoscopy (post double-blind treatment)	Research	Biopsies of esophagus
4	Fourth Endoscopy (post open-label treatment)	Research	Biopsies of esophagus

Study Visits:

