There are at least three visits during the screening period that will occur before enrollment and randomization to the active treatment phase of the SMILEE study. The timing of Visits 2 and 3 are not mandated as part of this study protocol, since these two visits are standard of care (during which study endpoint information is collected, Table 3). After confirmation of eligibility, subjects will be enrolled to the active phase of the study, randomized to study arms,

and treated with either Viaskin Milk EPIT or Viaskin placebo patch. Fully eligible subjects will be required to attend 17 study visits in total as follows:

- **Screening Period:**

- The GI collaborative team will help identify potentially eligible SMILEE study participants. Potentially eligible subjects will be enrolled to the study (Visit 1), to confirm Treatment Period study eligibility and obtain a number of study endpoints (see Table 3). The GI group will follow standard of care procedures, but the dates of the first (Visit 2) and second (Visit 3) endoscopies with biopsies will not be mandated by the investigative team, but by the GI group for clinical care. The second upper endoscopy/biopsy will be done at a minimum of 6 weeks after milk-removal, per clinical care. If a patient meets eligibility criteria for the Treatment Period of SMILEE, s/he will be referred to the Allergy / Immunology division for continuation in the study. If the results of the first or second endoscopy with biopsies confirm ineligibility, the subject may be considered as screen failed and may not continue in the study. However, if the GI group decides to obtain additional clinical care endoscopies with biopsies for confirmation or clarification of clinical diagnosis, results from these additional biopsies are allowed in the screening period (see Table 3, Study Flow Chart, below).
 - Visit 1: Informed Consent obtained. Milk introduction.
 - Visit 2: 1 week to 2 Months after milk-introduction. Standard of Care Upper endoscopy/Biopsy. Milk removed from the diet.
 - Visit 3: 6 weeks minimum after Milk-free diet. Standard of Care upper endoscopy/biopsy.
 - If a patient has endoscopies that confirm milk responsive EoE in the preceding 12 months, they will not need a repeat endoscopy to be eligible for the study.

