 - A minimum of two standard of care endoscopy procedures will be performed to obtain milk EoE diagnostic results needed for study qualification. Results from additional endoscopy procedures are allowed, if required for clinical purposes
 - Subjects' clinical care GI and Allergy physicians will determine the order of screening standard of care endoscopies.

- **Treatment Period:**

- Visit 4 (Day 1): Chart review, confirmation of eligibility. Randomization. Treatment start.
- Visit 5 (Day 8)
- Visit 6 (Month 1)
- Visit 7 (Month 3)
- Visit 8 (Month 6)
- Visit 9 (Month 9): Milk reintroduction.
- Visit 10: 1 week to 2 Months after milk reintroduction. (During this time, subjects will have weekly calls to monitor symptoms) End of double-blind treatment.
- Upper endoscopy/biopsy (research).

In addition, the patients could be contacted via telephone calls or email between visits to monitor symptoms, when symptoms reoccur-research endoscopy will be scheduled. The open-label treatment period will start on that day.

Open label Extension

- Visit 11: Day 8 after the Visit 10 research biopsy
- Visit 12: Month 1 after the Visit 10 research biopsy
- Visit 13: Month 3 after the Visit 10 research biopsy
- Visit 14: Month 6 after the Visit 10 research biopsy
- Visit 15: Month 9: 1 week to 2 months for milk reintroduction
- Visit 16: Upper endoscopy/biopsy (research)

• Last Assessment and End of Study Period/ Early Withdrawals:

- Visit 17: 2 weeks after Visit 16.

It is planned to randomize approximately 22 subjects in the study (16 Viaskin® Milk subjects and 6 Placebo subjects). A flowchart outlining study assessments and time of assessments is shown in Table 3. A schematic diagram of the study design is shown in Figure 1.

Table 3A: Study Flow Chart (Visits 1 to 10)

Study Assessments	Screening Period#			V4* *	V5	V6	V7	V8	V9	Double-blind Treatment Period	
	V1	V2*	V3							V10*	
	1 week to 2 months after Milk Re- Intod.	Minimu m 6 weeks after Removin g Milk	D1	D8 ± 3 days	M1 ± 7 days	M3 ± 14 days	M6 ± 14 days	M9 ± 14 days	Telephon e calls****	1 week to 2 month s after V9	
Informed Consent	X										
Medical History ¹	X										
Demographics ²	X										
Physical Examination ³	X	X	X	X	X	X	X	X	X		X
Vital signs ⁴	X	X	X	X	X	X	X	X	X		X
Quality of Life		X	X								X
Symptom Score	X	X	X	X	X	X	X	X	X		X
Laboratory Tests ⁶	X								X		X
Urine Pregnancy Test ⁷	X			X							X
Milk Introduction	X									X	X ¹⁰
Milk-free Diet		X [#]	X	X	X	X	X	X			

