8.3 Study Duration

The planned duration of the clinical study is approximately 3 years (Start-up + Screening period + Treatment period + Closeout). Subject participation will be approximately 2 years (including up to 3 months and 2 weeks screening period, 11 months treatment period, 11 month open label extension and 2-week follow-up). Recruitment into the study will stop when approximately 22 subjects have been randomized to treatment. The study will be stopped when the last subject receiving the double-blind treatment completes the study or when the last ongoing subject has discontinued treatment, whichever occurs first.

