13.6.8 Data and Safety Monitoring Board

A DSMB will be composed to review the safety and/or efficacy data of the study at any time judged necessary during the course of the study and after the first 3 patients are enrolled and then annually. Members of the DSMB will be selected and confirmed as early as possible, in any case before the first data review is convened. Ideally, the DSMB should be composed of experts in food allergy and in the methodology of clinical trials. The DSMB will review either blinded or unblinded data during the course of the study (see below). Various recommendations will then be made by the DSMB. The three members of the DSMB are [name], Chief of Allergy and Immunology, Arkansas Children's Hospital, Univ. of Arkansas School of Medicine; [name], PhD, Director of Eosinophilic Esophagitis Center, Rady's Children's Hospital, University of California at San Diego; and [name], Univ. of Colorado School of Medicine. Westat will supply blinded study results to the DSMB unless unblinded results are requested by the DSMB for safety reasons. For details of the emergency procedure for unblinding of individual subjects, see Section 8.5.10

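### The older-children-first step opens to ages 4-7 at the fourth randomization with no required safety review, and the one early DSMB look is tied to a different, ambiguous count

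*Protocol*

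**What the plan says.** **The age gate.** Protocol 8.1 gives the reason for the staging: "For safety purposes and to minimize risk, the first four patients will be 8-17 years old". It then says that "after these patients are randomized, we will open the study to all ages 4-17 years old". The Synopsis and SAP 2.1 repeat the rule without the reason. None of the three names a length of exposure, a completed visit or a DSMB decision that must come before the opening.

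**When randomization happens.** The visit list in Protocol 8.1 reads "Visit 4 (Day 1): Chart review, confirmation of eligibility. Randomization. Treatment start". Section 9.4 adds at least 3 hours of observation after that first patch, with skin grading and adverse event recording.

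**The DSMB.** Protocol 13.6.8 has the board review data "at any time judged necessary during the course of the study and after the first 3 patients are enrolled and then annually". It receives blinded results unless it asks for unblinded ones.

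**The word *enrolled*.** In the screening part of Protocol 8.1: "Potentially eligible subjects will be enrolled to the study (Visit 1". In the same section, after eligibility is confirmed: "subjects will be enrolled to the active phase of the study, randomized to study arms".

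**The concern.** A sentinel group protects the next group only if something is learned from it before the next group starts. Here the trigger is an allocation event. The rule is met on the day the fourth older child puts on a first patch, whatever has or has not been seen in the other three.

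The DSMB look that might supply the missing check is not connected to the gate. It counts three children instead of four. Its trigger word has two meanings, and on one of them the review could take place before any child has worn a patch.

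This matters because Protocol 6.4.3 describes the trial as the first pilot of this patch in eosinophilic esophagitis (EoE), and 8.5.6 says it uses the highest dose under development. Protocol 10.1 expects a systemic reaction, if one occurs, to appear as worsening EoE. My judgement is that a few hours of observation on Day 1 is poorly suited to showing that. The youngest children could therefore start without the information the staging was meant to provide.

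**Working it through.** The plan states no figure for this safeguard, so there is nothing to reproduce. The check is one of sequence, with a little arithmetic.

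**1. Data guaranteed when the gate opens.** Wear time is 6 h/day in week 1, 12 h/day in week 2 and 24 h/day from Day 15 (Protocol 8.5.1).
- Fourth child: the Day 1 application only, with at least 3 hours observed.
- First three children: each has had at least a first patch, but no minimum interval between randomizations is set.
- Scheduled wear before the 24-hour stage: 6 × 7 + 12 × 7 = 42 + 84 = 126 patch-hours. If the younger child's Day 1 falls less than 14 days after the first older child's Day 1, nobody has reached that stage.

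**2. How soon a 4-7 year old can start.**
- Full screening: at least 1 week on milk plus 6 weeks off, 7 + 42 = 49 days (taking the opening to mean opening at Visit 1). By then a fourth child on schedule is past Day 15 and past Visit 6 (Month 1 ± 7 days).
- Waiver: Protocol 8.1 drops repeat endoscopies when milk-responsive EoE was confirmed in the preceding 12 months. No minimum time to Visit 4 is then stated.

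**3. The gate and the DSMB look side by side.**

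| | Age gate (8.1) | First scheduled DSMB look (13.6.8) |
|---|---|---|
| Count | 4 | 3 |
| Event | randomized | enrolled |
| If enrolled = Visit 1 | – | may contain no treated child |
| If enrolled = randomized | – | follows the third treated child |
| Opening waits for it? | no | no |

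**4. How many sentinels are on active.** Allocation is 3:1, so 4 × 0.75 = 3 are expected. No block size is stated. Assuming unblocked allocation, the number is Binomial(4, 0.75), and P(2 or fewer) = 0.0039 + 0.0469 + 0.2109 = 0.26. Drawing instead from a fixed 16/6 list gives 0.0021 + 0.0437 + 0.2461 = 0.29. A first block of four would give exactly 3.

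**5. What four sentinels can show even with a review.** With 3 on active and no events, the one-sided 95% upper bound on the event rate is 1 − 0.05^(1/3) = 63%; with 4 on active it is 1 − 0.05^(1/4) = 53%. The chance that 3 active children show at least one event is 1 − 0.9³ = 27% at an assumed true rate of 10%, and 1 − 0.8³ = 49% at 20%. A review would find common problems only.

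**The case against.** The best defence is that other protections exist. Protocol 8.4.3.2 suspends enrolment pending expedited DSMB review after, for example, one related serious adverse event or two related Grade 3 events. The DSMB may also meet whenever it sees need. Protocol 6.4.2 cites a separate trial that tested doses up to 500 µg over 3 weeks, and Appendix 4 ties the dose to that trial's safety board. All of this stands, but none of it requires a look before ages 4-7 start. The stopping rules act only after a listed event, and the extra DSMB reviews are discretionary. The other trial is in IgE-mediated milk allergy, which this protocol excludes when active, and its results are not given.

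Two stronger readings are tempting and should be resisted.
- *A reader might infer that no patch data exist when the gate opens, so the staging protects nobody.* The documents do not support this. Randomization and first patch are the same visit, so all four older children should have had a first patch and its observation period. Full screening would add about seven weeks more.
- *A reader might infer that the early DSMB look must come before any treatment.* That takes only one sense of *enrolled*. Protocol 8.1 also uses the word for entry to the randomized phase, and on that sense the look follows the third treated child. The defect is ambiguity.

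**Conclusion.** The point holds. The age range opens on the fourth older child's Day 1, no review is required first, and the one early scheduled DSMB look has a different count and an undefined trigger. The worst case is a 4-7 year old starting on first-day data from the fourth older child, with no 24-hour wear in anyone. It needs two things that the protocol permits: closely spaced sentinels and the 12-month endoscopy waiver. With full screening the exposure problem largely goes away, but the missing review does not. The 26% chance of two or fewer sentinels on active holds only if allocation is unblocked.

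A reader might also infer that the first annual DSMB review comes after the last randomization, because "The planned duration of the clinical study is approximately 3 years". That does not follow. The longest stated participation is 3.5 + 11 + 11 + 0.5 = 26 months, so 36 − 26 = 10 months limits the last Visit 1. The last randomization could be as late as 36 − 22.5 = 13.5 months, and later with shorter individual durations. No start-up or close-out time is given.

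This is a cheap improvement to a safety safeguard. It does not touch the primary analysis.

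**What to change.** Reconcile the Synopsis, Protocol 8.1, Protocol 13.6.8 and SAP 2.1:
1. State in 13.6.8 which sense of *enrolled* applies.
2. Tie the first scheduled DSMB review to the same four children as the age gate, and to a milestone that carries patch safety data.
3. Make the opening to ages 4-7 conditional on that review.

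The sponsor and DSMB should choose the milestone; no exposure threshold is proposed here. The cost is a wording amendment and a short wait for ages 4-7, during which older children continue to enrol. The sample size and the analyses stay as they are.

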8.2 Discussion of Study Design

The current study is a pilot study powered to show statistical significance versus placebo. The design of this study is based on standard procedures used in clinic practice.

This study is also randomized and double-blinded with regard to treatment with Viaskin® Milk and matching placebo in order to prevent bias in treatment allocation and in the assessment of both safety and efficacy. The use of a placebo group in this trial is justified to obtain reliable scientific evidence for the evaluation of new medicinal products. The overall benefit to risk ratio for this trial is favorable. Subjects eligible to participate in this study must have a positive upper endoscopy with biopsy showing greater than or equal to 15 eosinophils/hpf when on milk containing diet, and that normalized (0-10 eosinophils/hpf) when milk was removed from the diet. The prospect of direct benefit is resolution of food allergy in EoE, which will be the first cure in the disease. The risk of the trial is due to the Viaskin® Milk EPIT patch, which resulted in non-serious adverse events in the phase 1 trial. The other risks are one research upper endoscopy with biopsies under sedation or general anesthesia, which the investigative team believes is a minor increase above minimal risk procedure when done by board certified gastroenterologist. The second risk is reoccurrence of EoE symptoms in placebo group or non-responders. Therefore, we have incorporated a period of 1 week to 2 month to milk re-exposure to minimize symptoms of EoE. The primary endpoint in this study will be assessed at the end of the treatment period, after up to 11 months of EPIT treatment. After the initial double-blind phase, all subjects will receive open-label active treatment for up to additional 11 months for collection of safety and efficacy data.

8.3 Study Duration

The planned duration of the clinical study is approximately 3 years (Start-up + Screening period + Treatment period + Closeout). Subject participation will be approximately 2 years (including up to 3 months and 2 weeks screening period, 11 months treatment period, 11 month open label extension and 2-week follow-up). Recruitment into the study will stop when approximately 22 subjects have been randomized to treatment. The study will be stopped when the last subject receiving the double-blind treatment completes the study or when the last ongoing subject has discontinued treatment, whichever occurs first.

8.4 Study Population

Pediatric subjects (4 to 17 years old) with milk-induced Eosinophilic Esophagitis will be randomized in this study.

8.4.1 Inclusion Criteria

Subjects **MUST** satisfy all of the following entry criteria:

1. Subjects between 4 and 17 years of age at the time of signing the informed consent.
2. Well-documented symptoms suggestive of EoE after ingestion of milk and currently following a strict milk-free diet.
3. Upper endoscopy and biopsy at clinical evaluation during screening showing greater than or equal to 15 eosinophils/HPF isolated to the esophagus meeting the consensus diagnosis of Eosinophilic Esophagitis, after milk was re-introduced into the subject's diet (30 ml/day for 1 week to 2 months), while the subject was on proton pump inhibitor (PPI). Patients will be on PPI for the length of the study as that is standard of care for the treatment of EoE. A clinical decision has been made to perform a minimum of two standard of care endoscopy procedures to obtain milk EoE diagnostic results.
4. Upper endoscopy and biopsy at clinical evaluation during screening showing 0 to 10 eosinophils per HPF isolated to the esophagus after a minimum of 6 weeks under milk-free diet, and while the subject is on proton pump inhibitor. (Standard of care for EoE is an upper endoscopy with biopsies to evaluate for disease activity). A clinical decision has been made to perform a minimum of two standard of care endoscopy procedures to obtain milk EoE diagnostic results.
5. Negative pregnancy test for female subjects of childbearing potential. Females of childbearing potential must use effective method of contraception to prevent pregnancy and agree to continue to practice an acceptable method of contraception for the duration of participation in the study. Sexual abstinence will be accepted as an effective method of contraception for girls below 18 years of age.
6. Subjects and/or parents/guardians willing to comply with all study requirements during their participation in the study.
7. Signed informed consent from parent(s)/guardian(s) of children < 18 years + children's assent.
8. Subjects agree to maintain a constant diet during the trial, with the exception of milk.
9. Subjects will maintain constant medications for asthma and allergic rhinitis during the trial.

8.4.2 Exclusion Criteria

If any of the following apply, the subject **MUST NOT** enter the study:

1. Subjects with a history of severe anaphylaxis to milk with the following symptoms: hypotension, hypoxia, neurological compromise (collapse, loss of consciousness or incontinence), Quincke Edema or requiring intubation.
2. Active IgE- mediated milk allergy based on skin test or history.
3. Pregnancy or lactation.
4. Subjects with other eosinophilic gastrointestinal disorders.
5. Subjects on swallowed corticosteroids or anti-leukotrienes for Eosinophilic Esophagitis.
6. Subjects with symptomatic allergy to pollens whose symptoms during the corresponding pollen season might interfere with the recording of symptoms during the upper endoscopy/biopsy, if the upper endoscopy/biopsy is conducted during the pollen season. The Investigator will have to ensure that the period for conducting the upper endoscopy for such a subject will be outside of the pollen season.
7. Subjects treated with systemic long-acting corticosteroids (depot corticosteroids) within 12 weeks prior to Visit 1 and/or systemic short-acting corticosteroid within 4 weeks prior to Visit 1 or any systemic corticosteroid at screening.
8. Subjects with asthma conditions defined as follows:

- a. Uncontrolled persistent asthma by National Asthma Education and Prevention Program Asthma guidelines (2007).
- b. At least two systemic corticosteroid courses for asthma in the past year or one oral corticosteroid course for asthma in the past three months;
- c. Prior intubation for asthma in the past two years.
9. Subjects on β -blocking agents, angiotensin-converting enzyme inhibitors, angiotensin-receptor blockers, calcium channel blockers or tricyclic antidepressant therapy.
10. Subjects undergoing any type of immunotherapy to any food (oral immunotherapy, sublingual immunotherapy, specific oral tolerance induction) within one year prior to Visit 1.
11. Subjects presently on aeroallergen immunotherapy and unwilling or unable to discontinue.
12. Subjects currently treated with anti-tumor necrosis factor drugs or anti-IgE drugs (such as omalizumab) or any biologic immunomodulatory therapy within one year prior to Visit 1.
13. Allergy or known hypersensitivity to the Viaskin[®] patch material or excipients.
14. Allergy or known history of reaction to Tegaderm[®] with no possibility to use an alternative adhesive dressing allowed by the Principal Investigator.
15. Subjects suffering from generalized dermatologic diseases (e.g. severe atopic dermatitis, uncontrolled generalized eczema, ichthyosis vulgaris) with no intact skin zones to apply the Viaskin[®], or urticarial and mast cell disorders such as chronic idiopathic urticaria.
16. Subjects (or parents of subjects) with obvious excessive anxiety and unlikely to cope with the conditions of an upper endoscopy and biopsy.
17. Past or current disease(s), which in the opinion the Principal Investigator, may affect the subject's participation in this study including but not limited to active autoimmune disorders, immunodeficiency, malignancy, uncontrolled diseases (hypertension, psychiatric (especially anxiety), cardiac), or other disorders (e.g., liver, gastrointestinal, kidney, cardiovascular, pulmonary disease, or blood disorders).
18. Any history of drug or alcohol abuse in the past five years.
19. Subjects unable to follow the protocol and the protocol requirements.
20. Participation in another clinical intervention study in the three months prior to Visit 1.
21. Subjects on any experimental drugs or treatments.

